#### Handling of Missing Data

Every attempt will be made to collect all protocol required data at each time point.

Imputations will only be performed for efficacy data and for missing or partial dates, missing severity or relationship to investigational product. Missing AE or CM dates and missing severity or relationship to study drug will always use a conservative approach. Details will be included in the SAP.

For subjects who discontinue treatment (for any reason), subjects will continue to be followed and key efficacy endpoints and safety data collected where possible.

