## 15.4. Handling of Missing Data

Every attempt will be made to collect all protocol required data at each time point.

Imputations will only be performed for efficacy data and for missing or partial dates, missing severity or relationship to investigational product. Missing AE or CM dates and missing severity or relationship to investigational product will always use a conservative approach. Details will be included in the SAP.

For subjects who discontinue treatment (for any reason), subjects will continue to be followed and key efficacy endpoints and safety data collected where possible.

The primary analyses for change in bilateral UEMS will use a mixed model repeated measures which automatically accounts for the missing data based upon the covariate structure assumed. To evaluate robustness of results, sensitivity analyses will be performed with imputation methods for missing data.

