7.3 Handling of Dropouts and Missing Data

Except for the data specified below, missing data will not be imputed.

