8.8.2 Adverse Events

All adverse events (AEs) recorded on the eCRF will be coded using the MedDRA dictionary [Version 22.0 (or a later version if updated during the study)] and classified as pre-treat AEs, or treatment-emergent AEs as follows:

- Pre-treat AEs are events that start prior to the date of first dose of study treatment;
- TEAEs are events with start date on or after the date of first dose of study treatment, or with a start date prior to the date of first dose of study treatment whose severity worsens on or after the date of first dose of study treatment. TEAEs will be limited to those events occurring within 28 days after the last injection of study treatment, with AEs occurring after that being defined as post-treatment. AEs with missing start date after applying imputation rules will be considered as TEAEs.

Assessment of AE severity will be based on the Common Terminology Criteria for Adverse Events (CTCAE, version 5.0). Missing severity will not be imputed.

The relationship between an AE and study treatment is assessed as definitely, probably, possibly, unlikely, or not related. A treatment-related AE is an AE considered by the investigator as definitely, possibly, or probably related to study treatment or with unknown/missing relationship to study treatment.

All AE data will be listed. Treatment-emergence status will be flagged in the listing. In addition, corresponding listings of serious AEs (SAEs), AEs leading to discontinuation from study, AEs of special interest, and AEs resulting in death will be produced. Summary tables of TEAEs by dose cohort for Part 1 or by treatment group for Part 2 and overall will be produced.

An overview table will summarize the number and percentage of subjects with at least one of the following TEAEs, where subjects with more than one TEAE in a particular category are counted only once in that category:

- Any TEAE;
- TEAE by maximum severity;
- Treatment-related TEAE;
- TEAE leading to discontinuation from study;
- TEAE of Special Interest;
- Serious TEAE;
- Treatment-related serious TEAE;
- Serious TEAE leading to discontinuation from study;
- Serious TEAE leading to death.

The number of total TEAEs will be also included in the overview table.

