The number and percentage of subjects reporting each TEAE will be summarized by SOC and PT, or PT. Tables will be sorted in descending overall frequency by SOC, and then in descending overall frequency by PT within SOC, and then alphabetically. The following summaries will be produced:

- TEAEs, by SOC and PT;
- TEAEs, by PT;
- TEAEs, by SOC and PT and maximum severity;
- Treatment-related TEAEs, by SOC and PT;
- Lumbar Puncture procedure related TEAEs, by SOC and PT (Part 2 only);
- TEAEs leading to discontinuation from study, by SOC and PT;
- TEAEs of Special Interest, by SOC and PT;
- Serious TEAEs, by SOC and PT;
- Treatment-related serious TEAEs, by SOC and PT;
- Lumbar Puncture procedure related serious TEAEs, by SOC and PT (Part 2 only);
- Serious TEAEs leading to discontinuation from study, by SOC and PT;
- Serious TEAEs leading to death, by SOC and PT.

In the above summaries, subjects with more than one AE within a particular SOC are counted only once for that SOC. Similarly, subjects with more than one AE within a particular PT are counted only once for that PT. For summaries by maximum severity, subjects with multiple AEs within a particular SOC or PT will be counted under the category of their most severe AE within that SOC or PT.

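### The SAP leaves missing adverse event severity unimputed, although the protocol says it will be imputed conservatively, and the departure is not declared

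*SAP*

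**What the plan says.** Protocol section 15.4 limits imputation to a short list that includes severity: "Imputations will only be performed for efficacy data and for missing or partial dates, missing severity or relationship to investigational product". It then sets the direction: "Missing AE or CM dates and missing severity or relationship to investigational product will always use a conservative approach". The details are left to the SAP. The synopsis has the same commitment: "Missing AE or CM dates and missing severity or relationship to study drug will always use a conservative approach".

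SAP section 7.3 sets the default: "Except for the data specified below, missing data will not be imputed". Its two subsections cover dates and efficacy endpoints only. Section 8.8.2 then deals with severity directly: "Missing severity will not be imputed".

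The same section treats the neighbouring items differently. An event counts as treatment-related if it is graded possibly, probably or definitely related, "or with unknown/missing relationship to study treatment". For dates, "AEs with missing start date after applying imputation rules will be considered as TEAEs".

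Severity is used in two places in 8.8.2: a line in the overview table and a summary of "TEAEs, by SOC and PT and maximum severity". In the latter, a subject with several events in a class or term is placed under the worst of them. Table 6 (section 8.1) adds a Missing category to summaries whenever at least one group has a missing value.

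**The concern.** The protocol left the SAP to say how missing severity would be imputed. It did not leave open whether it would be. The SAP's answer is that it will not be, which goes beyond filling in detail.

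It also looks like an oversight. Missing relationship and missing start date are both resolved in the cautious direction in the same section, and severity alone is not. A deliberate change should appear in section 9, which lists changes from the protocol-specified analyses.

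Safety and tolerability against placebo is a primary objective of Part 2 (protocol 6.2.1), and the maximum-severity summaries are part of the evidence for it. Compared with a rule that counts ungraded events as severe, leaving them ungraded can only lower the reported severe rate or leave it unchanged.

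**Working it through.** The plan states no figure on this point, so there is none to reproduce. The check is a comparison of rules, followed by one line of arithmetic for scale.

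**Rules side by side**

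| Missing item | Protocol 15.4 and synopsis | SAP | Agree? |
|---|---|---|---|
| Event start date | Impute, conservatively | Partial dates imputed (7.3.1); if still missing, treated as treatment-emergent (8.8.2) | Yes |
| Relationship | Impute, conservatively | Counted as related (8.8.2) | Yes |
| Severity | Impute, conservatively | Not imputed (8.8.2) | No |

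**Is the change declared?** SAP 9.1 to 9.3 cover a secondary endpoint, exploratory endpoints and analysis populations. SAP 10.1 to 10.3 cover post hoc efficacy analyses and the slope model. Neither section mentions severity.

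**What happens to a subject in the maximum-severity table**

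- One ungraded event and no other: shown as Missing under Table 6.
- One mild and one ungraded event in the same class: shown as mild or as Missing. The SAP does not say which.
- One severe and one ungraded event in the same class: counted as severe through the graded event.

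Only the first two kinds of subject would be placed differently under a rule that counts missing as severe.

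**Scale**

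Inputs: about 16 subjects per arm (protocol 15.1), and k, the number of subjects in an arm whose only potentially severe event is ungraded. The documents do not give k, so the range below is an assumption.

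Change in that arm's severe rate = 100 × k/16 percentage points.

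- k = 0: 0 points
- k = 1: 100 × 1/16 = 6.25 points
- k = 2: 100 × 2/16 = 12.5 points

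**The case against.** The strongest reply is that almost nothing depends on this. Investigators are to grade events by CTCAE (protocol 14.2.5.1), so there may be no missing grades at all. Safety analysis is descriptive and has no hypothesis tests (protocol 15.3 and 15.11). Stopping decisions rest on judgment about individual events (protocol 7.3.3.1 and 7.3.3.2), not on this table. The summaries of serious events, events of special interest, discontinuations and deaths do not use the severity grade. All of this stands, and it keeps the point small.

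Three stronger readings are tempting, and the documents do not support them.

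- A reader might infer that ungraded events are dropped or downgraded, so that the rule is the reverse of conservative. Table 6 should show them openly as Missing, and all adverse events are listed.
- A reader might infer that any subject with an ungraded event cannot be counted as severe. The table counts subjects by their worst event, so another severe-graded event in the same category is enough.
- A reader might infer that the protocol requires missing severity to be counted as Grade 3. It names no grade and does not define conservative handling for severity.

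There is also a fair objection to imputing severe. It labels every ungraded event as severe, including minor ones. If missing grades are uneven between arms, it can distort the comparison in either direction.

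The contradiction remains after all this. A Missing row is transparent, but it is not the imputation the protocol promises. It also leaves the ranking of Missing undefined when the maximum is taken.

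**Conclusion.** The point holds as an undeclared contradiction between protocol and SAP on a single rule. A subject whose only potentially severe event is ungraded will not be counted as severe in the maximum-severity summaries. The SAP also leaves undefined where such a subject goes when a milder graded event is present.

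The effect is 6.25 percentage points per affected subject in an arm of about 16, and zero if every event is graded. This rests on two assumptions: the planned arm size, and the reading of conservative as counting missing severity towards the severe end. The second is the usual reading, but it is an inference. The documents do not show that any safety conclusion would change. The point is minor and worth correcting mainly because the correction is cheap and carries out the protocol's own commitment.

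**What to change.** In SAP 8.8.2, replace the sentence on missing severity with a rule such as:

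> *In the maximum-severity summaries, an adverse event with missing severity will be counted as severe (Grade 3) in both treatment groups. Listings will show the value as missing. The number of events with missing severity will be reported by treatment group.*

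Grade 3 is a proposal, since the protocol names no grade. Reporting the count by arm lets a reader see how far the rule affects the comparison.

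If the sponsor prefers no imputation, section 9 should list and justify the departure, and 8.8.2 should state how Missing ranks against graded events when the maximum is taken.

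SAP section 10 records that Day 169 data have been unblinded and analysed, and section 2.2 planned safety summaries at that stage. Either change should therefore be dated and disclosed as made after unblinding. A fixed rule applied identically to both arms leaves little room for bias.

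The cost is a few sentences, plus a rerun of the affected safety tables if any grade is missing. The downside is that some minor ungraded events may be shown as severe. Data collection and the efficacy analyses are unaffected.

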## 15.11. Safety Endpoints

The safety analysis will be descriptive in nature. All safety data will be listed, and data will be tabulated by dose (Part 1) and treatment group (Part 2) where the data warrant. Safety data include:

- AEs, including assessment of lumbar infusion site
  - Events occurring prior to the first dose of investigational product or placebo will be defined as pre-treatment events.

- For Part 1, TEAEs will be defined as any AE occurring during or after the injection of study drug. This will therefore include all events occurring through Day 29/ET.
- For Part 2, TEAEs will be limited to those events occurring within 28 days after the last visit.

Incidence of AEs will be summarized for each treatment group/cohort by MedDRA system organ class (SOC) and preferred term, sorted in descending frequency by SOC, and then by preferred term within SOC. These summaries will be given by treatment in separate tables for each of the following TEAE event sets:

- All events
- Treatment related events (defined by a relationship to study drug of possible, probable, or definite).
- Serious adverse events
- Events leading to premature discontinuation from study
- Events by maximum severity
- AEs of Special Interest, ie, events relating to the lumbar puncture procedure (eg, infection, headache, back pain, excessive CSF leakage requiring blood patch).

Other safety outcomes will include:

- Clinical laboratory tests, including hematology, chemistry, metabolic, and urinalysis. Changes over time will be presented. Potentially clinically significant (PCS) ranges will be defined and used to determine the incidence of subjects experiencing newonset PCS laboratory values, where new-onset is defined as a PCS value for a subject following initiation of study treatment for which the subject did NOT have a PCS value for that analyte PRIOR to initiation of study treatment.
- Vital signs including: respiratory rate or pulse oximetry, heart rate, temperature, and blood pressure, as per the schedule of events. BMI will be assessed, with height collected only at screening.
- Physical examination
- 12-lead ECG. ECG parameters will be analyzed in a fashion similar to that of clinical laboratory parameters.

Condition-specific safety outcomes will include:

- ISNCSCI, GRASSP and all of the neurological measures evaluated for efficacy

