8.2 Subject Disposition and Data Sets Analyzed

For Part 1, subject disposition will be listed and summarized by dose cohort and overall for the Safety population and will include the number and percentage of subjects that are included in each study population (Safety Population, FAS, PK analysis set, and ADA analysis set). For Part 2, subject will be listed and summarized by treatment group and overall for the All Randomized Set and will include the number and percentage of subjects included in each study population (Safety Population, mITT, PK analysis set, ADA analysis set, and PPS).

In addition, the number and percentage of subjects who complete the study and who discontinue early, including a breakdown of the primary reasons for discontinuation, will be presented.

8.3 **Protocol Deviations**

All protocol deviations for Part 1 will be listed.

For Part 2, Protocol deviation will be identified prior to database lock and unblinding. All protocol deviations will be listed. All important protocol deviations that impact the interpretation of efficacy outcome measures, leading to exclusion from the PPS, will be summarized by treatment group and overall for the mITT. Number and percentage of subjects with at least one important protocol deviations including a breakdown of type of protocol deviations will be summarized.

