8.8.1 Extent of Exposure

Exposure data for the study treatment will be listed for both Part 1 and Part 2.

For Part 2, the following variables will be summarized for each treatment group:

- Treatment duration: Treatment duration (days) is defined as the date of last infusion the date of first infusion +1.
- Number of infusions
- Cumulative dose: cumulative dose is defined as the sum of all doses taken during treatment period.
- Type of modification including drug interrupted, withdrawn, reduced, delayed/not given, or rate changed.

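### Part 2 adverse events are tabulated by whether they led to leaving the study, so no planned table shows which ones stopped or interrupted dosing

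*SAP*

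**What the plan says.** **Adverse events.** The overview table in SAP 8.8.2 has a row for "TEAE leading to discontinuation from study" and a second row for the serious events among these. The tables include "TEAEs leading to discontinuation from study, by SOC and PT" and "Serious TEAEs leading to discontinuation from study, by SOC and PT". The listings to be produced include "AEs leading to discontinuation from study, AEs of special interest, and AEs resulting in death will be produced". Protocol 15.11 sets the same category: "Events leading to premature discontinuation from study". Protocol 9.1 defines a discontinuation as ceasing to take part in the study.

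**Disposition.** SAP 8.2 presents "the number and percentage of subjects who complete the study and who discontinue early", with the primary reasons for discontinuing. Protocol 15.8 likewise summarises completion and withdrawal.

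**After dosing stops.** Protocol 15.4 states: "For subjects who discontinue treatment (for any reason), subjects will continue to be followed", with key efficacy and safety data gathered where possible. SAP 7.3.2 repeats the rule. Protocol 7.1.2 and SAP 2.2.2 schedule the Day 137 call and the Day 169 and 253 visits after the last dose or after dosing ends early.

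**Exposure.** For Part 2, SAP 8.8.1 summarises treatment duration, number of infusions and cumulative dose by arm, and "Type of modification including drug interrupted, withdrawn, reduced, delayed/not given, or rate changed".

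**The concern.** Part 2 plans six intrathecal doses, and safety and tolerability of repeat dosing against placebo is a primary objective (SAP 2.1.2.1). How often an adverse event ends or interrupts dosing is a direct measure of tolerability. By design, stopping dosing and leaving the study are different events here, but the adverse event outputs record only the second. A subject whose dosing ends because of an adverse event, and who then attends the remaining visits as the protocol intends, counts as a study completer and appears in no table of events leading to discontinuation.

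**Working it through.** No alpha, power or effect size is involved, and the plan gives no figure to reproduce. The check is a count of outputs, a trace of two subjects through them, and one percentage.

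**Step 1: discontinuation outputs in SAP 8.8.2.**
- Listings: 1.
- Overview rows: 2 (any event, serious event).
- Tables by system organ class and preferred term: 2 (any, serious), out of 12 summaries listed.
- Total: 1 + 2 + 2 = 5. All five refer to leaving the study. None refers to stopping treatment, and none to a skipped, interrupted, delayed or reduced dose.

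**Step 2: do the documents foresee dosing stopping without study exit?** Yes.
- Protocol 15.4, SAP 7.3.2, protocol 7.1.2 and SAP 2.2.2 provide for follow-up after treatment stops.
- The liver-test rule in protocol 14.1.5 requires treatment to stop and does not mention leaving the study.
- The same section has laboratory findings that change or stop the drug recorded as adverse events.
- SAP Table 3 lists receiving fewer than five doses and leaving the study as separate intercurrent events.

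**Step 3: trace two hypothetical subjects.** Each receives two doses and then attends Days 169 and 253. Subject A stops dosing because of an adverse event. Subject B stops because too little cerebrospinal fluid can be collected (protocol 11.2.2 allows the dose to be skipped, and has dosed subjects complete the remaining visits with no further lumbar puncture attempts). Subject B also has some unrelated adverse event.

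| Output | Subject A | Subject B |
|---|---|---|
| Disposition (SAP 8.2) | Completer | Completer |
| Infusions given (SAP 8.8.1) | 2 of 6 | 2 of 6 |
| Modification type (SAP 8.8.1) | Counted, no cause stated | Counted, no cause stated; may be the same type |
| Per Protocol Set (SAP 6.7, at least 5 doses) | Excluded | Excluded |
| General adverse event tables (SAP 8.8.2) | Event counted | Event counted |
| Five discontinuation outputs (SAP 8.8.2) | Absent | Absent |

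The planned tables can therefore treat the two subjects alike, although only subject A bears on whether the drug is tolerated.

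**Step 4: size.** With 16 subjects per arm (protocol 7.2), one subject is 1/16 = 6.25 percentage points of the arm.

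**The case against.** The strongest reply is that little is hidden. An adverse event that stops dosing still enters the general tables by class, term and severity and, where it qualifies, the treatment-related, lumbar puncture-related, special-interest and serious tables. All adverse event data are listed. The dosing change is summarised by arm in SAP 8.8.1, and Per Protocol Set membership is reported by arm. With about 32 subjects, a reader could compare the adverse event and exposure listings. The SAP also follows the protocol's own category, so it departs from nothing. All of this stands, and it limits the point to a missing link between event and dosing change.

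Three stronger readings are tempting, and the documents do not support them.
- A reader might infer that the adverse event drops out of the report. It does not.
- A reader might infer that good retention drives the discontinuation tables to zero whatever the drug does. Protocol 9.1 allows withdrawal from the study for safety and requires withdrawal for an adverse event to be distinguished, while protocol 15.4 promises follow-up only where possible. Some events can therefore still reach those tables.
- A reader might infer that a zero there would be false. It would be correct for the quantity named, which is leaving the study. The documents give no expected rate of stopping dosing for adverse events, so no figure for a hidden rate can be stated.

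The reply does not supply the link itself. Comparing listings by hand is not a planned summary by arm, and the exposure counts do not separate causes.

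**Conclusion.** The point holds as a cheap improvement to safety reporting, mainly for Part 2, since Part 1 gives a single dose. The event and the dosing change are each reported, but adverse-event-driven stopping or interruption of dosing cannot be read from any planned table. It is a gap shared by protocol and SAP, not a conflict between them.

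The size is 6.25 percentage points of an arm for each affected subject who stays in follow-up, assuming 16 per arm. How many such subjects there are is unknown. A subject who also leaves the study because of the same event is already captured. The conclusion concerns tabulation only and takes no view on any rule for stopping treatment.

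**What to change.** For Part 2, add two categories to the SAP 8.8.2 overview, the tables by system organ class and preferred term, and the listings:
- treatment-emergent adverse events leading to discontinuation of study treatment;
- treatment-emergent adverse events leading to a dose being skipped, interrupted, delayed or reduced.

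Keep the existing rows for leaving the study. In SAP 8.2, report treatment discontinuation with its primary reason separately from study discontinuation.

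The cost is a few extra descriptive tables. Safety data are not hypothesis-tested (protocol 15.3), so nothing inferential changes. SAP section 10 records changes made after the Day 169 unblinding, so these outputs should be labelled there as added.

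One condition affects the effort. The documents do not show whether the adverse event page of the eCRF records the action taken with study treatment. If it does, no new data are needed. If it does not, the link must be derived from adverse event and dosing records for about 32 subjects, and the derivation rule should be written down.
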